3.1. Background

Basal or premixed insulins are the recommended insulin starters following oral antihyperglycemic medication (OAM) failure in Chinese patients according to guidelines released by the Chinese Diabetes Society (CDS 2013). Premixed insulins contain rapid- and intermediate-acting insulin that control fasting (preprandial) and postprandial glucose (PPG) elevations, respectively. In many Asian countries, including China, patients initiate insulin therapy with premixed insulins (CDS 2013). In fact, over 50% of Chinese T2DM patients initiated insulin therapy with premixed insulin while less than 20% patients initiated with basal insulin (Ji et al. 2009; Ji et al. 2011). Two main causes may contribute for this phenomenon. Firstly, in patients with high PPG, which is a characteristic of Asian patient population, treatment with mixtures provides additional benefits by controlling PPG elevation (Kalra et al. 2010). Secondly, a great proportion of Chinese patients need more aggressive insulin regimen due to delay in diagnosis or insulin initiation. Patients who require intensive insulin treatment may prefer premixed insulin with a less number of injections per day to basal bolus regimen (Jia et al. 2015). Generally speaking, although some physicians believe that basal insulin once daily is more suitable for patients with mild or moderate hyperglycemia following OAM failure while premixed insulin twice daily is more suitable for patients with moderate or even more severe hyperglycemia, the perception about efficacy and safety profile between premixed insulin analog and basal insulin analog is comparable in China.

Currently, 2 classes of insulin analog mixtures are available in the China market based on different formulations: low mixtures with low ratio of rapid acting insulin like insulin lispro 75/25 and insulin aspart 70/30, or mid mixtures with equal ratio of rapid acting insulin and intermediate acting insulin like insulin lispro 50/50 and insulin aspart 50/50. Most of the physicians selected low mixtures analog as start insulin in their practice. The reasons probably are that insulin analog mid mixtures went on the market after low mixtures and physicians are more familiar with premixed human insulins which are more commonly provided as low mixed formulation and have been used for a long time in China. At the same time, basal insulin analogs, including levermir and glargine, are also widely used in China.

The F3Z-CR-IOQI (IOQI) (CLASSIFY) study is a Phase 4, randomized, open-label, multinational and multicenter trial (Watada et al. 2016). It showed that LM25 and LM50 were noninferior to each other in improving glycemic control in East Asian patients with T2DM. Additionally, LM50 was more efficacious than LM25 with respect to the percentage of subjects

reaching target hemoglobin A1c (HbA1c) levels. In China subgroup which accounts for around 40% of the whole study population, LM50 is superior to LM25 in HbA1c change (-2.03% versus -1.55%) from baseline, and a significantly higher percentage of patients achieved HbA1c levels of <7% (72.4% versus 45.0%; P=0.001) levels in the LM50 treatment group compared to the LM25 treatment group, while no increased hypoglycemia incidence or more weight gain is observed in LM50 group as trade-off (Su et al. 2015a). The better response to LM50 in the Chinese population is probably due to the pronounced high PPG which reflects Chinese patient's venerable beta cell function and high carbohydrate intake diet (Su et al. 2015b; Chen et al. 2016).

This evidence is of great value in helping physician's select insulin regimens, but it is the sole multicenter clinical trial supporting the use of insulin analog mid mixture as start insulin. More investigation is needed on mid mixtures as starter insulin in East-Asia patients.

3.3. Benefit/Risk Assessment

More detailed information about the known and expected benefits and risks of study insulin treatments may be found in the package inserts of these insulin products.

4. Objectives and Endpoints

Table IOQR.2 shows the objectives and endpoints of the study.

Table IOQR.2. Objectives and Endpoints

Objectives	Endpoints
Primary	
1. To compare change in HbA1c from baseline to 24 weeks between insulin analog mid mixture BID and basal insulin analog QD treatments	1. The change in HbA1c from baseline to 24 weeks
Secondary	
2. To compare change in HbA1c from baseline to 48 weeks between insulin analog mid mixture BID and basal insulin analog QD treatments	2. The change in HbA1c from baseline to 48 weeks
3. To compare the proportion of patients who achieve HbA1c <7% at 24 and 48 weeks between insulin analog mid mixture BID and basal insulin analog QD treatments	3. Proportion of patients who achieve HbA1c <7% at 24 and 48 weeks
4. To compare the change in venous FPG from baseline to 24 and 48 weeks between insulin analog mid mixture BID and basal insulin analog QD treatments	4. Venous FPG change from baseline at 24 and 48 weeks
5. To compare the change in FSBG-based FBG and PPG from baseline to 24 and 48 weeks between insulin analog mid mixture BID and basal insulin analog QD treatments	5. FSBG-based FBG, PPG change from baseline at 24 and 48 weeks
6. To compare the daily insulin dose at 24 and 48 weeks between insulin analog mid mixture BID and basal insulin analog QD treatments	6. Daily insulin dose at 24 and 48 weeks
7. To compare the change in body weight from baseline to 24 and 48 weeks between insulin analog mid mixture BID and basal insulin analog QD treatments	7. Body weight change from baseline at 24 and 48 weeks
8. To compare the severe, nocturnal and total hypoglycemia incidences and rates during the 24-week and 48-week treatment period between insulin analog mid mixture BID and basal insulin analog QD treatments	8. The severe, nocturnal and total hypoglycemia incidences and rates during the 24-week and 48-week treatment period

Objectives and Endpoints

Objectives	Endpoints
9. To compare time to insulin treatment change between insulin analog mid mixture BID and basal insulin analog QD treatments	
9. Time to insulin treatment change: Defined as time to any of: insulin treatment discontinuation, switch, intensification or reduction in frequency
 
Discontinuation: Defined as stopping insulin treatment for 30 days or more.
 
Switch: Defined as stop the initial insulin therapy and started another insulin therapy of different class.
 
Intensification: Defined as any of the following: adding meal time insulin in basal insulin analog QD group; changing from BID to TID in insulin analog mid mixture BID group
 
Reduction in frequency: Defined as any of the following: changing from BID to QD; changing from TID to BID or QD

10. To compare the proportion of patients who achieve the HbA1c <7% without switching and discontinuing study insulin, and without using rescue therapy between insulin analog mid mixture BID and basal insulin analog QD treatments	10. Proportion of patients who achieve the HbA1c <7% without switching and discontinuing study insulin, and without using rescue therapy
11. To compare the patients-reported self-efficacy related to insulin therapy as assessed using SEITQ between insulin analog mid mixture BID and basal insulin analog QD treatments	11. The change in SEITQ score form baseline at 48 weeks
Tertiary/Exploratory	

12. To compare the insulin treatment pattern for
 
 • discontinuation • switch • intensification • reduction in frequency 
between insulin analog mid mixture BID and basal insulin analog QD treatments
	
12. Time to insulin discontinuation, switch, intensification or reduction in frequency
 
Proportion of patients who experience insulin discontinuation, switch, intensification or reduction in frequency during 48 weeks

13. To compare healthcare resource utilization (all-cause and T2DM-related; inpatient, outpatient and ER) between insulin analog mid mixture BID and basal insulin analog QD treatments	13. Healthcare resource utilization (all-cause and T2DM-related; inpatient, outpatient and ER) during 48 weeks
14. To compare patients' perception of insulin treatment satisfaction , as assessed using the ITSQ at 24 and 48 weeks between insulin analog mid mixture BID and basal insulin analog QD treatments	14. Domain and total ITSQ score at 24 and 48 weeks
15. To compare the patients-reported self-efficacy related to insulin therapy as assessed using SEITQ between insulin analog mid mixture BID and basal insulin analog QD treatments	15. The change in SEITQ score form baseline at 24 weeks

Objectives and Endpoints

Objectives	Endpoints
16. To compare the incidences and rates of other categories of hypoglycemia (documented symptomatic, asymptomatic, unspecified, probable symptomatic and relative hypoglycemia), if available, during the 24-week and 48-week treatment period between insulin analog mid mixture BID and basal insulin analog QD treatments	16. The incidences and rates of other categories of hypoglycemia (documented symptomatic, asymptomatic, unspecified, probable symptomatic and relative hypoglycemia), if available, during the 24-week and 48-week treatment period

Abbreviations: BID = twice daily; FBG = fasting blood glucose; FPG = fasting plasma glucose; FSBG =finger stick blood glucose HbA1c = hemoglobin A1c; ITSQ = Insulin Treatment Satisfaction Questionnaire; PPG = post prandial glucose; QD = once daily; SEITQ = Self-efficacy about Insulin Therapy Questionnaire; T2DM = type 2 diabetes mellitus; TID = three times daily.

5. Study Design

5.1. Overall Design

Study F3Z-GH-IOQR (IOQR) is a multicenter, randomized, 48-week, parallel, 2-arm pragmatic trial in Chinese patients with T2DM who have failed to achieve adequate glycemic control with OAMs comparing the effectiveness of insulin analog mid mixture BID and basal insulin analog QD treatments in real world setting.

Figure IOQR.1 illustrates the study design.

[figure not shown]

Figure IOQR.1. Illustration of study design for Pragmatic Study F3Z-GH-IOQR.

5.2. Number of Participants

Approximately 830 participants will be randomized 1:1 into the 2 treatment groups such that there will be approximately 664 evaluable participants for primary analyses at Week 24

5.3. End of Study Definition

End of the trial is the date of the last visit or last scheduled procedure shown in the Schedule of Activities (Section 2) for the last patient.

5.4. Scientific Rationale for Study Design

Given the results of the previous IOQI randomized clinical trial, this pragmatic study is designed to demonstrate that the results drawn from the randomized clinical trial can be applied in more generalizable populations and real world settings.

According to the scientific questions raised, instead of a randomized clinical trial (RCT) or a prospective observational study, a PCT is selected because the study aims to compare effectiveness in real world settings with minimal intervention while randomization is required to remove selection bias and other confounding factors between arms.

Two arms including basal insulin analog, and insulin analog mid mixture will be compared in a Chinese general T2DM population. The following considerations have been incorporated into study design to ensure a robust study that represents real world situations:

- Restriction on inclusion and exclusion criteria for patients in this study is minimal compared with a typical RCT. Patients enrolled will represent a general T2DM population with uncontrolled HbA1c levels under OAM.
- There is also no restriction on insulin titration algorithm and OAM use. Also there is no restriction on switching or augmenting the initial insulin treatment. Physicians can pursue their general practice governed by local guideline.
- The schedule of visits is aimed to reflect real-world practice. In general, the frequency of visits to physician offices after insulin initiation is weekly or biweekly in a real world setting for dose titration and adjustment (CDS 2013). Therefore, the potential intervention brought by the scheduled monthly or every 3 month visits could be considered minimal.
- The duration of this study is 48 weeks which is relatively longer than a typical RCT with 24 or 26 weeks comparing 2 insulin regimens by measuring HbA1c. So adequate information from real world settings could be observed and collected.
- In China, the community based primary care health system is not well developed, and most of the patients go to see the endocrinologists to start insulin treatment instead of general practitioners. Therefore in this study, no community based clinical center will be selected as study sites.

In summary, the study design presented is intended to provide a better understanding of the real-world feasibility and performance of initiating insulin treatment with insulin analog mixtures.

5.5. Justification for Dose

No dose range assessment exists for this trial, therefore this is not applicable. This is a pragmatic trial and insulin titration will be determined by individual investigator as would occur in clinical practice setting.

6. Study Population

Prospective approval of protocol deviations to recruitment and enrollment criteria, also known as protocol waivers or exemptions, are not permitted.

6.1. Inclusion Criteria

Patients are eligible to be included in the study only if they meet all of the following criteria at enrollment:

- [1] have type 2 diabetes as defined by World Health Organization (WHO) criteria ([Appendix 2](#))
- [2] are ≥ 18 and ≤ 80 years of age at the time of Visit 1
- [3] are taking OAMs and are judged as OAM failure by the investigator
- [4] most recent HbA1c value $\geq 7.5\%$ within 12 weeks of study entry
- [5] in the opinion of the investigator, require to initiate premix analog or basal insulin analog treatment
- [6] willing to start with insulin treatment
- [7] are able and willing to give signed informed consent ([Appendix 3](#))

6.2. Exclusion Criteria

Patients will be excluded from study enrollment if they meet any of the following criteria at enrollment:

- [8] have a diagnosis of type 1 diabetes
- [9] have received any type of insulin within 24 months of study entry (except for intermittent use of insulin of less than 1 month each time)
- [10] have serious preexisting medical or other conditions that, in the judgment of the investigator, would preclude participation in this study.
- [11] are pregnant or breastfeeding, or intend to become pregnant during the course of the study
- [12] are currently enrolled or have participated, within the last 30 days in any other clinical trial involving an investigational product or any other type of medical research judged not to be scientifically or medically compatible

6.3. Lifestyle Restrictions

Not applicable.

6.4. Screen Failures

Individuals who do not meet the criteria for participation in this study (screen failure) may not be rescreened.

7. Treatments

7.1. Treatments Administered

This study involves a comparison of insulin analog mid mixture BID and basal insulin analog QD in routine care.

No drug will be provided, but drug treatments expected for this trial are:

- Insulin analog mid mixture: for example, Humalog Mix50, Novorapid 50
- Basal insulin analog: for example, insulin glargine, insulin detemir

After randomization to initial insulin treatment regimen, treatment decisions will be solely at the discretion of the physician and the patient, and anti-hyperglycemia treatment will be conducted within the construct of the standard care according to CDS guideline (CDS 2013).

Investigational products are defined as insulins being used in this study.

The investigator or his/her designee is responsible for the following:

- explaining the correct use of the investigational products to the patient or care givers.
- verifying that instructions are followed properly

7.1.1. Packaging and Labelling

All study drugs are commercially available. Study drug will not be supplied to patients.

7.2. Method of Treatment Assignment

Patients who meet all criteria for enrollment will be randomized to treatment/intervention at Visit 1. Assignment to treatment groups will be determined by a computer-generated random sequence using an interactive voice-response system (IVRS) or interactive web-response system (IWRS) and then the site will be responsible for providing the treatment/intervention to the patients.

7.2.1. Selection and Timing of Doses

The dose will be initiated, titrated and maintained at the discretion of the investigator following the usual standard of care according to CDS guideline (CDS 2013).

The timing of doses will follow product labels.

7.3. Blinding

This is an open-label study.

7.4. Dosage Modification

Dose adjustments are at the discretion of investigator following usual standard of care.

7.5. Preparation/Handling/Storage/Accountability

The healthcare professionals (HCPs) are responsible to ensure the safe handling and appropriate storage of the investigational products.

7.6. Treatment Compliance

No patient-reported and HCP-perceived compliance of the treatment will be assessed.

7.7. Concomitant Therapy

All concomitant therapies that are part of routine care are allowed and can be used during the study.

Only anti-hyperglycemic concomitant therapy will be collected at baseline and throughout the study (Section 2).

7.8. Treatment after the End of the Study

7.8.1. Study Extensions

Not applicable.

7.8.2. Continued Access

The insulin analogs used in this study are commercially available in China.

7.8.3. Special Treatment Considerations

Rescue therapy for hyperglycemia and hypoglycemia will be determined by the investigator following usual standard of care.

7.8.4. Patient Follow-Up in Pragmatic Trials

Patient follow-up is dictated only by usual care, no additional visit is required by the protocol.

8. Discontinuation Criteria

8.1. Discontinuation from Study Treatment

8.1.1. *Permanent Discontinuation from Study Treatment*

Not applicable due to the pragmatic nature of this trial.

8.1.2. *Temporary Discontinuation from Study Treatment*

Not applicable due to the pragmatic nature of this trial.

8.1.3. *Discontinuation of Inadvertently Enrolled Patients*

Not applicable due to the pragmatic nature of this trial.

8.2. Discontinuation from the Study

Patients will be discontinued from study in the following circumstances:

- Exclusion criteria: [10], [11] or [12] is/are observed or develop(s) after study entry or enrollment.

Some possible reasons that may lead to permanent discontinuation include:

- enrollment in any other clinical trial involving an investigational product or enrollment in any other type of medical research judged not to be scientifically or medically compatible with this study
- participation in the study needs to be stopped for medical, safety, regulatory, or other reasons consistent with applicable laws, regulations, and good clinical practice (GCP)
- investigator decision
 - the investigator decides that the patient should be discontinued from the study
- subject decision
 - the patient or the patient's designee, for example, parents or legal guardian requests to be withdrawn from the study

Patients who discontinue from the study early will have end-of-study procedures performed as shown in the Schedule of Activities (Section 2).

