9.2.1. Serious Adverse Events

An SAE is any AE from this study that results in one of the following outcomes:

- death
- initial or prolonged inpatient hospitalization
- a life-threatening experience (that is, immediate risk of dying)
- persistent or significant disability/incapacity
- congenital anomaly/birth defect
- considered significant by the investigator for any other reason: important medical events that may not result in death, be life-threatening, or require hospitalization may be considered serious, based upon appropriate medical judgment.

Although all AEs occurring after signing the ICF are recorded in the CRF, serious adverse event (SAE) reporting begins after the patient has signed the ICF and has received investigational product. However, if an SAE occurs after signing the ICF, but prior to receiving investigational product, it needs to be reported ONLY if it is considered reasonably possibly related to study procedure.

Study site personnel must alert Lilly or its designee of any SAE within 24 hours of investigator awareness of the event via a sponsor-approved method. If alerts are issued via telephone, they are to be immediately followed with official notification on study-specific SAE forms. This 24-hour notification requirement refers to the initial SAE information and all follow-up SAE information.

Pregnancy (during maternal or paternal exposure to investigational products) does not meet the definition of an AE. However, to fulfill regulatory requirements any pregnancy should be reported following the SAE process to collect data on the outcome for both mother and fetus.

Investigators are not obligated to actively seek AEs or SAEs in subjects once they have discontinued and/or completed the study (the patient summary CRF has been completed). However, if the investigator learns of any SAE, including a death, at any time after a subject has been discharged from the study, and he/she considers the event reasonably possibly related to the study treatment or study participation, the investigator must promptly notify Lilly.

Investigators or other study personnel are requested to report adverse reactions in temporal association with Lilly drugs not under evaluation and with any non-Lilly drugs to the appropriate

party (for example, regulators or local market authorization holder) as they would in normal practice as required by applicable laws, regulations, and practices.

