10.3. Statistical Analyses

10.3.1. General Statistical Considerations

Statistical analysis of this study will be the responsibility of Lilly or its designee. Any change to the data analysis methods described in the protocol will require an amendment only if it changes a principal feature of the protocol. Any other change to the data analysis methods described in the protocol, and the justification for making the change, will be described in the statistical analysis plan (SAP) or the clinical study report (CSR). Additional exploratory analyses of data will be conducted, as deemed appropriate.

Given the nature of this pragmatic study, both efficacy and safety analyses will be performed on randomized patients. As sensitivity analyses, certain efficacy analyses may be repeated by censoring all efficacy data after patients changed the randomized treatment regimen.

All tests of treatment effects will be conducted at a 2-sided alpha level of 0.05, unless otherwise stated.

The baseline value for measurements will be defined as the last non-missing observation on or before the randomization visit. If no data are available, the baseline value will be treated as missing. The Week 24 value for measurements will be the last non-missing post-baseline observation up to 24 weeks, and the Week 48 value for measurements will be the last non-missing post-baseline observation up to 48 weeks.

For continuous measures, summary statistics will include at least the number of patients with data, mean, SD, median, minimum, and maximum. For categorical measures, summary statistics will include at least the number of patients with data, frequency counts, and percentages. For comparisons based on analysis models, the differences will be reported using LS means, along with 95% CIs and p-value. Sometimes, comparison on the summary statistics may be performed and p-values be provided, and such p-values should be viewed as a descriptive measure only. Unless specified otherwise, a two-sample t-test will be used for continuous measurements and Fisher's exact test will be used for categorical measurements.

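### Protocol 8.2 removes randomised patients from the study by rule when exclusion [10], [11] or [12] arises later, so scheduled outcomes after one early-termination visit are lost without need

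*Protocol*

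**What the plan says.** Protocol 8.2 opens with "Patients will be discontinued from study in the following circumstances" and lists one circumstance: "Exclusion criteria: [10], [11] or [12] is/are observed or develop(s) after study entry or enrollment". The removal is from the study, not only from insulin.

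The three criteria are in Protocol 6.2:
- [10] covers patients who "have serious preexisting medical or other conditions that, in the judgment of the investigator, would preclude participation in this study".
- [11] covers those who "are pregnant or breastfeeding, or intend to become pregnant during the course of the study".
- [12] covers current or recent participation in another investigational-product trial, or in incompatible research.

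Protocol 8.2 then lists enrolment in another trial a second time, among reasons that are only possible grounds for leaving.

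A patient who leaves early has the end-of-study procedures once. The Schedule of Activities places the early-termination (ET) visit within 14 days of the decision. It marks HbA1c, FPG, two-point finger-stick glucose, weight, insulin treatment and dose, adverse events, hypoglycemia, SEITQ, ITSQ and resource use. After that, Protocol 9.2.1 says: "Investigators are not obligated to actively seek AEs or SAEs in subjects once they have discontinued".

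Elsewhere, Protocol 7.1 states that no drug is supplied and that, after randomisation, "treatment decisions will be solely at the discretion of the physician and the patient". Protocol 8.1 answers each item on stopping study treatment with "Not applicable due to the pragmatic nature of this trial". Protocol 10.3.1 says that "both efficacy and safety analyses will be performed on randomized patients".

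**The concern.** Criteria [10] to [12] are sensible at entry. Applied after randomisation, they remove patients because of later events, and some of those events could depend on the assigned regimen. Criterion [10] also rests on the judgement of an investigator who knows the arm, so removal could differ between arms. Its text concerns preexisting conditions while Protocol 8.2 applies it to new ones, so sites may read it differently.

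Protocol 5.4 says the trial is randomised to remove selection bias and aims at a general T2DM population. Because care is usual care, remaining in the study mainly means remaining under data collection. The loss of later outcomes is therefore created by the rule, and it falls mostly on the 48-week endpoints.

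**Working it through.** **1. The plan's own figures.** Inputs from Protocol 10.1 and SAP section 5: SD 1.5, margin 0.4, true difference 0, 332 evaluable per arm, 20% dropout, two-sided alpha 0.05.
- SE = 1.5 × √(2/332) = 0.1164. The 95% CI half-width = 1.96 × 0.1164 = 0.228.
- The half-width is below 0.4, so at least one non-inferiority statement always holds. This agrees with the stated figure of more than 99%.
- Non-inferiority in one named direction has power 93.0%.
- 332 / 0.80 = 415 per arm, as stated; 830 × 0.80 = 664, as stated.

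**2. Numbers affected.** The documents give no rate of removal under 8.2. Assume 1% to 10% of each arm is removed under the rule, falls within the 20% dropout allowance, and would otherwise have a Week 24 HbA1c.
- 415 × 0.01 = 4 and 415 × 0.10 = 42 patients per arm.
- Keeping them raises the evaluable number from 332 to between 336 and 374 per arm. The half-width falls from 0.228 to between 0.227 and 0.215, and one-direction power rises from 93.0% to between 93.3% and 95.4%.
- The sample size does not need to change.

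**3. Bias in the Week 24 difference.** Approximate bias = (excess fraction removed in one arm) × (difference in HbA1c change between unobserved and observed patients). Both inputs are assumptions.
- Smallest case: 0.01 × 0.5 = 0.005 points.
- Largest case: 0.05 × 2.0 = 0.10 points.

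With an observed difference of 0, the upper limit is 0.228, so a shift of 0.4 − 0.228 = 0.172 is needed to reach the margin. The HbA1c difference in unobserved patients that would produce it is 0.172 / excess:

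| Excess removed in one arm | Difference needed (points) |
|---|---|
| 2% | 8.6 |
| 5% | 3.4 |
| 10% | 1.7 |
| 20% | 0.86 |

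This takes the ET HbA1c as not counting for Week 24. The documents are unclear on that. Protocol 10.3.1 would accept the latest value before Week 24. Protocol 10.3.3.1 and SAP 8.2.1 describe a single Week 24 measurement without imputation. The SAP Appendix 1 window closes at a Visit 4 date that a patient removed earlier does not have. If the ET value counts, those patients have an earlier measurement in place of the Week 24 one.

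**4. What happens to each later endpoint.**
- *Week 48 HbA1c:* not measured. SAP 8.2.2 either carries an earlier value forward or, in the MMRM, leaves it missing under a missing-at-random assumption.
- *Time to insulin treatment change:* Protocol 10.3.3.2 and SAP 8.2.2 censor at early discontinuation, which treats leaving as unrelated to the risk of a change.
- *Hypoglycemia:* the yearly rate has an exposure offset (Protocol 10.3.4, SAP 8.4.4). The incidence comparison is Fisher's exact test and has none.
- *Resource use over 48 weeks:* proportions are compared by Fisher's exact test (SAP 8.3.2), again without adjustment. A patient whose ET visit falls at Week 12 is observed for 12/48 = 25% of the period but counts fully in the denominator.

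**The case against.** The strongest reply is that the rule is narrower than it looks and that a good deal is still collected. Most of this stands.

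- A reader might infer that any serious illness forces a patient out. It does not. Criterion [10] needs a judgement that participation is precluded, so a hospitalisation does not trigger it by itself.
- A reader might infer that data stop when the illness begins. They do not. The ET visit records HbA1c, adverse events, hypoglycemia and resource use up to that point. Protocol 9.2 keeps the investigator responsible for following serious adverse events until they resolve, stabilise or are explained. Protocol 9.2.1 still requires notice of related serious events learned of later, and reporting of pregnancies.
- A reader might infer that the rule removes the patients with the worst course. That fits [10] at most. Pregnancy, intending pregnancy or joining another trial does not imply worse control.
- Protocol 7.1 and 8.1 concern treatment while 8.2 concerns participation, so there is no direct contradiction between them. Analysing randomised patients does not forbid withdrawals, and 20% dropout is planned. Protocol 3.2 also accepts that a pragmatic trial may keep some experimental features.
- Resource use is an exploratory endpoint.

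What remains is that removal is mandatory once a criterion is met, no scheduled outcome follows the ET visit, and the plan gives no reason why data collection must end in a trial that supplies no drug.

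**Conclusion.** The point holds as a cheap improvement. Protocol 8.2 produces avoidable, possibly differential missing data after the ET visit, mainly in Week 48 HbA1c, time to insulin treatment change, 48-week hypoglycemia incidence and resource use. The size of the effect on those endpoints cannot be computed, because the documents give no removal rate.

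For the primary endpoint the shift is about 0.005 to 0.10 points against a 0.4 margin, assuming 1% to 5% excess removal and a 0.5 to 2.0 point HbA1c difference. The documents do not support a claim that the rule on its own threatens the non-inferiority conclusion. It could matter for a superiority reading if a confidence limit lies close to 0.

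Separately, Protocol 8.2 makes other-trial enrolment a mandatory reason through [12] and an optional one in the list that follows. The two must be reconciled.

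**What to change.** Amend Protocol 8.2 so that [10], [11] or [12] arising after randomisation is recorded with its date and the patient's arm. Scheduled outcome data (HbA1c at Weeks 24 and 48, insulin regimen, hypoglycemia, resource use, adverse events) would then continue to be collected where consent, the investigator's medical or safety judgement, and regulation allow. Reconcile the mandatory and optional statements on other-trial enrolment in the same amendment.

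Do not add a rule that withdraws patients later found ineligible. Protocol 8.1.3 treats that situation as not applicable, and such a rule would be a new post-randomisation exclusion. Clinical care stays with the physician as in Protocol 7.1.

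The cost is a short amendment and a notice to sites. Some retained HbA1c values will reflect pregnancy, intercurrent illness or another trial's treatment. These can be flagged and left out in a sensitivity analysis.
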